## 8.2 Secondary Endpoints

### Markers of inflammation

We will compare the proportion of patients who achieve reduction in FCP to less than 250ug/g and by greater than 50% from baseline. Fecal concentration of calprotectin, a calcium binding protein found in neutrophilic granulocytes, will be measured by LabCorp. FCP concentration is correlated with endoscopic findings of mucosal inflammation and decreases following initiation of medications in active CD. There is no single standard to define mucosal healing with FCP; a recent meta-analysis identified 250 µg/g as the optimal cut point for endoscopically defined inflammation among patient with IBD. There are a number of important reasons to measure FCP in this study. From the patient's perspective, FCP predicts the risk of recurrence of symptoms for those who have achieved clinical remission through medical or surgical therapy. Equally as important, to achieve optimal adoption of dietary strategies into the management of CD will require convincing treating physicians of the effectiveness of the diet. Increasingly, physicians are demanding evidence that CD treatments improve inflammation in addition to symptoms. Thus, FCP is a biomarker that predicts an important outcome for patients and for physicians it can be used to document reduction in mucosal inflammation.

We will use hsCRP as a marker of systemic inflammation. We can compare the proportion of patients who have hsCRP below the upper limit of normal and mean levels of hsCRP as outcome measures.

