**Analysis of secondary outcomes (Secondary Aim 2):**

The secondary outcomes of clinical remission as assessed by the CDAI, PRO2, PRO3 reduction of hsCRP by >50% and to <5 mg/L, reduction of FCP by >50% and to a value of <250mcg/g and combined clinical remission and resolution of inflammation will be analyzed using the same methods described for the primary outcomes.

The secondary outcomes of fatigue, sleep quality, social aspects and pain interference will be measured using PROMIS short forms using the same methods as previously employed within CCFA Partners. PROMIS items are calibrated using a T score such that 50 is the mean for the general US population with a standard deviation of 10. Higher scores reflect greater level of the domain. We will compare PROMIS scores at baseline and at the end of the trial using a t-test. If there are meaningful differences in baseline scores between the treatment arms, comparison of the PROMIS measures at the end of follow-up will be adjusted for the baseline value using linear regression.

**Analysis of data from weeks 7 – 12 (Secondary Aim 3):** After week 6, participants will need to provide for the meals on their own if they choose to remain on the diet. This provides an opportunity to further assess the combined feasibility of the diets in the real world and patients' satisfaction with following the diet. Utilizing results from 24-hour dietary recalls, we will determine the proportion of patients assigned to each arm who elect to remain on the diet through week 12. We will also determine the proportion of patients who were able to discontinue steroid use by week 12 among the subgroup who were taking steroids in weeks 1-6. Finally, we will assess reasons for discontinuation of the diet among those who did not continue. Comparisons will be made using the CMH test following the principle of intention to treat. The analysis will be repeated among the subgroup of participants who achieved remission by week 6. These results will be qualitatively compared to the free text data on satisfaction and personal experience with the diets.

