### 2. Overview

This is a randomized, multicenter, comparative effectiveness trial of the specific carbohydrate diet (SCD) and a Mediterranean style diet (MSD) to induce remission in patients with Crohn's disease. The study is funded by PCORI, will be conducted in up to 50 centers throughout the United States over a period of three years.

The primary and secondary objectives of this clinical trial are the following:

*Primary:*

1. To compare the effectiveness of the specific carbohydrate diet and a Mediterranean style diet to induce symptomatic and clinical remission in patients with Crohn's disease.
- 2.
3. *Secondary:*
  1. To compare the effectiveness of the specific carbohydrate diet and a Mediterranean style diet to reduce mucosal inflammation in patients with active Crohn's disease. Mucosal inflammation will be assessed by measuring the concentration of calprotectin in the feces (FCP).
  2. To compare the effectiveness of the Specific Carbohydrate Diet and a Mediterranean style diet to reduce systemic inflammation in patients with active Crohn's disease. Systemic inflammation will be assessed by measuring the concentration of C reactive protein (CRP).
  3. To compare the effectiveness of the specific carbohydrate diet and a Mediterranean style diet to improve the following symptoms in patients with Crohn's disease: a) fatigue, b) pain, c) joint symptoms.
  4. To determine the proportion of patients who continue the study diets when prepared food is no longer provided without cost and the reasons for discontinuation of the diets.

The clinical trial will enroll 194 participants who will be randomly assigned in a 1 to 1 ratio to the two study diets. The main inclusion criteria are Crohn's disease with mild to moderately active symptoms as measured by the short CDAI (sCDAI) score greater than 175 and less than 400, and at least 18 years of age. The main exclusion criteria are the following:

- Pregnancy
- Hospitalized pts. or surgery planned within 6 wks
- Ostomy or known symptomatic intestinal stricture
- Start of thiopurines, natalizumab, vedolizumab or methotrexate (w/in 12 wks) or anti-TNF (w/in 8 wks)
- Start or change corticosteroids within 1 week of screening or dose >20mg prednisone or equivalent
- Use of antibiotics w/in 2 weeks of screening
- Start or change of dose of 5-ASA type medication w/in 2 weeks of screening
- Baseline stool frequency >4 bowel movements/day when well
- BMI<16 or ≥40

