## 5.2. Sample size

The study is designed to enroll 97 patients into each of the treatment arms. Specific aims 1 and 2 will be considered separately and no reduction in type 1 error will be applied for multiple testing. The anticipated remission rate in the group receiving the MSD is unlikely to exceed 40% given the historical remission rates in placebo arms of Crohn's disease trials and assuming only a modest therapeutic benefit of this less restrictive of the two diets. Sample size calculations assume no loss to follow-up since all participants who are lost to follow-up will be categorized as non-responders in the analyses of both dichotomous primary outcomes (symptomatic remission and reduction in mucosal inflammation). Our PPRN Patient Governance Council met and determined that the minimum clinically important difference in remission rates is 20% as smaller differences are unlikely to justify the challenges of following a strict restriction diet such as the SCD. Thus, we used an anticipated remission rate of 40% with the MSD and 60% with the SCD to determine the sample size. With 97 participants per group, the study will have 80% power with a type 1 error of 5% to detect a difference of 40% vs 60% in effectiveness of the two diets using a chi test.

In reality, we anticipate that the remission rate in the MSD will be less than 40%. The power curve shown below depicts the power to detect a 20% difference based on the remission rate in the MSD arm of the trial where  $p_1$  represents the remission rate in the SCD arm (i.e.,  $p_1=0.3$  represents power to detect a difference of 10% vs 30% across a sample size ranging from 60 to 120). With 97 participants per group, there is more than 90% power to detect a difference of 10% vs 30% and 80% power to detect a difference of 40% vs 60%.

Finally, all of the power estimates are likely slight under estimates. We expect even more power when the Cochran-Mantel-Haenszel (CMH) chi test is used since we expect that the odds ratios in different strata are in the same direction.

Viewed alternatively, with 97 participants per arm, there is 80% and 90% power to detect the following differences based on the effectiveness of the control diet (i.e. the MSD).

Proportion of MSD group achieving the outcome	80% power to detect an absolute difference (SCD - MSD) greater than or equal to	90% power to detect an absolute difference (SCD - MSD) greater than or equal to
10%	15%	18%
20%	18%	21%

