##### 5.5.1.3.1. Reduction in systemic inflammation

Reduction in systemic inflammation based on measurement of hsCRP will be defined as having a final hsCRP <5mg/L and >50% reduction from the baseline hsCRP concentration.

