Analysis of secondary outcomes (Secondary Aim 1): hsCRP data will be analyzed in the same manner as FCP data.

Analysis of secondary outcomes (Secondary Aim 2): The secondary outcomes of clinical remission as assessed by the CDAI, PRO2, PRO3 and combined clinical remission and resolution of inflammation will be analyzed using the same methods described for the primary outcomes. We will compare PROMIS scores at baseline and at the end of the trial using a t-test. If there are meaningful differences in baseline scores between the treatment arms, comparison of the PROMIS measures at the end of follow-up will be adjusted for the baseline value using linear regression.

Analysis of data from the Extension Phase (Secondary Aim 2): After week 6, participants will need to provide for the meals on their own if they choose to remain on the diet. This provides an opportunity to further assess the combined feasibility of the diets in the real world and patients' satisfaction with following the diet. Utilizing results from 24-hour dietary recalls, we will determine the proportion of patients assigned to each arm who elect to remain on the diet through week 12. We will also determine the proportion of patients who were able to discontinue steroid use by week 12 among the subgroup who were taking steroids in weeks 1-6. Finally, we will assess reasons for discontinuation of the diet among those who did not continue. Comparisons will be made using Fisher's exact test following the principle of intention to treat. The analysis will be repeated among the subgroup of participants who achieved remission by week 6. These results will be qualitatively compared to the free text data on satisfaction and personal experience with the diets.

Change from baseline stratified by treatment arm: For continuous outcome measures, such as sCDAI, PRO2, PRO3, and FCP, we will compare the week 6 and week 12 values to the baseline value using the Wilcoxon sign rank test, a nonparametric paired test. These analyses will be conducted separately for each treatment group. Imputation of missing data for this analysis will assume that the worst case scenario that the outcome measure was worse during follow-up than at baseline. (Note that approach to missing data for other analyses are described below).

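### The hsCRP outcome differs between protocol 8.2 and protocol 8.4.2/SAP, and no between-diet analysis of hsCRP concentration is specified

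*Combined protocol and SAP*

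**What the plan says.** Secondary objective 2 (protocol 2.3, repeated in SAP section 2) asks whether the diets differ in reducing systemic inflammation, as assessed by the concentration of CRP. Blood for hsCRP is drawn at baseline, week 6 and week 12 (protocol 7.6).

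The outcome built from these measurements is described in several places:

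- Protocol 8.2, markers of inflammation: "We can compare the proportion of patients who have hsCRP below the upper limit of normal and mean levels of hsCRP as outcome measures". No scale, test or visit is given.
- Protocol 8.4.2, secondary outcomes: "reduction of hsCRP by >50% and to <5 mg/L", analysed by the method for the primary outcome, a Cochran-Mantel-Haenszel test.
- SAP 5.5.1.3.1: reduction in systemic inflammation "will be defined as having a final hsCRP <5mg/L and >50% reduction from the baseline hsCRP concentration".
- SAP 5.5.2, Secondary Aim 1: "hsCRP data will be analyzed in the same manner as FCP data". For FCP, that is a responder comparison.

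Both documents also plan signed-rank tests of change from baseline for continuous measures. These are done within each arm separately, and the examples listed include FCP but not hsCRP. Protocol section 2 calls the secondary aims exploratory. No power is stated for any hsCRP analysis.

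**The concern.** The objective is framed on a concentration, but the only hsCRP comparison between diets with a stated method is a yes/no outcome with two cuts. That outcome discards the size of the change and makes limited use of the baseline value. It also fits part of the population awkwardly. Entry requires an hsCRP result but no minimum value, so a participant who enters at 4 mg/L is a failure unless the value more than halves. The FCP analysis excludes participants with baseline FCP below 250 mcg/g. The SAP does not say whether analysing hsCRP like FCP carries a similar exclusion across.

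Two things are at stake. The analyst can choose between three descriptions of the outcome. And the report may not say by how much CRP concentration differed between diets, although the data to answer that will have been collected.

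**Working it through.** **1. The plan's own power figure.** The inputs are "The study is designed to enroll 97 patients into each of the treatment arms" and a two-sided 5% test. With n per arm, rates p1 and p2, and m their average, power = Φ{[|p2 − p1|√n − 1.96√(2m(1 − m))] / √(p1(1 − p1) + p2(1 − p2))}.

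- 40% vs 60%: (0.2 × 9.849 − 1.96 × 0.7071) / 0.6928 = 0.843, so power is 80.0%. The SAP states 80%.
- 10% vs 30%: (0.2 × 9.849 − 1.96 × 0.5657) / 0.5477 = 1.572, so power is 94.2%. The SAP states more than 90%.

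Both figures reproduce. They concern the primary endpoint; there is no hsCRP figure to reproduce.

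**2. Assumptions for hsCRP.** None of these is in the documents. Baseline and week-6 values are log-normal with baseline median 3, 6 or 12 mg/L; SD of log hsCRP 0.8, 1.2 or 1.5; correlation 0.5 or 0.7; SCD:MSD ratio 0.80, 0.65 or 0.50, the same for everyone. Both arms share a 15% fall, there is no dropout, and each arm has 97 participants. That gives 3 × 3 × 2 × 3 = 54 scenarios, each simulated 1,500 times, with a simulation error of about 1 to 2 points. A chi-square test stands in for the stratified test.

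**3. One scenario by hand** (median 6, log-SD 1.2, correlation 0.5, ratio 0.65).

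- *Log scale, baseline-adjusted.* SE = 1.2 × √(1 − 0.5²) × √(2/97) = 0.1492. |ln 0.65| = 0.4308. Power = Φ(0.4308/0.1492 − 1.96) = Φ(0.927) = 82%.
- *Responder.* The MSD week-6 median is 6 × 0.85 = 5.10 mg/L. The SD of log change is 1.2√(2 × 0.5) = 1.2, and its correlation with log week-6 hsCRP is 0.5. The bivariate normal probability of meeting both cuts is 23.7% on MSD. On SCD (median 5.10 × 0.65 = 3.32 mg/L) it is 37.3%. The formula in step 1 gives (0.1358 × 9.849 − 1.96 × 0.6513) / 0.6442 = 0.094, so power is 54%.
- *Simulation.* Log-scale 82%, responder 53%, t-test on untransformed week-6 means 45% (1,000 runs). A separate run at median 5 gave 84%, 56% and 44%.

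**4. All 54 scenarios, difference in power against the responder in all randomised participants.**

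| Comparison | Range (points) | Count |
|---|---|---|
| Log-scale, baseline-adjusted | 0 to +49 | at least 12 points in 34; negative in 0 |
| Untransformed week-6 mean | −40 to +13 | lower than the responder in 44 |
| Untransformed change | −60 to +8 | lower than the responder in 52 |

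The log-scale gain is about zero where both methods have power near 100%. It is also small where both have little: at median 3, log-SD 1.5, correlation 0.5 and ratio 0.80 it is 8 points (21% against 13%).

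If the responder analysis were limited to baseline hsCRP of at least 5 mg/L, the log-scale gain would be 0 to 61 points. The untransformed mean would then be lower than the responder in only 23 of 54.

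**5. Departures from a constant effect of that size.** At a ratio of 0.85, gains were 3 to 19 points in one set of runs and 5 to 11 in another. With the effect confined to baseline above 5 mg/L, one set reached 12 points in 7 of 24 scenarios and gave −1 to +5 at median 3. Another gave about 0 to 27.

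**The case against.** The responder is a reasoned choice. The plan prefers dichotomous outcomes with dropouts counted as failures, the SAP expressly extends the FCP approach to hsCRP, and 5 mg/L is the hsCRP cut that protocol 8.4.2 uses to define baseline inflammation. The secondary aims are exploratory and carry no power claim. The simulations in which log-scale regression does best use that method's own model. All of this stands, and it is why the responder proportion need not be displaced.

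It does not settle the inconsistency within the protocol, and it does not supply an analysis of level. An exploratory aim is served by an estimate with an interval, and a responder rate does not say how far concentrations differ.

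A reader might also infer that the protocol plans an arithmetic mean on the raw scale, which the SAP then drops at a cost in power. The documents do not support this. Protocol 8.2 is permissive and names no scale. The double cut is already in protocol 8.4.2, so the protocol disagrees with itself before the SAP is reached. And moving from untransformed means to the responder in all randomised participants usually raises power on skewed data.

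**Conclusion.** The point holds as an inconsistency and an omission: 8.2 does not match 8.4.2 or the SAP, and no between-diet analysis of hsCRP concentration is specified. Relative to a log-scale, baseline-adjusted comparison, the responder costs 0 to about 50 points of power under the constant-effect assumptions above. The cost is smaller, possibly nil, if the effect is weaker or limited to raised baselines.

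There is no guaranteed minimum loss. In a narrower set of assumptions (median 3 to 8, log-SD 1.0 to 1.4, ratio 0.65 to 0.75) the smallest gain was 12 points. A reader might take that as a floor, but 20 of the 54 wider scenarios fall below it. Nor do the documents show that a real difference is likely to be missed, since they give no hsCRP distribution or effect. This is an inexpensive improvement to a secondary analysis and does not threaten the trial's main conclusion.

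**What to change.** Reconcile protocol 8.2 with protocol 8.4.2 and SAP 5.5.1.3.1 so that all name the same hsCRP outcomes. Replace the reference to mean levels in 8.2, and add to SAP 5.5.2 (Secondary Aim 1), this sentence: *Week-6 (and week-12) log hsCRP will be compared between diets by linear regression on arm, baseline log hsCRP and biologic-therapy stratum, reported as a ratio of geometric means with 95% CI.* Report it alongside the existing responder proportion. Which of the two is called the main hsCRP analysis is a matter of preference.

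In the same edit, say whether the upper limit of normal in 8.2 means 5 mg/L and whether any baseline exclusion applies to hsCRP. Also say how values below the assay's reporting limit enter the logarithm. The plan's existing rule for missing continuous secondary outcomes (baseline carried forward, with sensitivity analyses) can apply.

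The cost is wording, one extra model and an effect measure less familiar than a responder rate. No new data or participants are needed.

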### Secondary clinical outcomes and combined outcomes

As a secondary outcome, we will assess the proportion of patients achieving combined clinical remission and reduction in FCP using the same criteria described above.

As a secondary clinical outcome, we will measure the Crohn's Disease Activity Index (CDAI) at baseline, 6 weeks and 12 weeks. Clinical remission will be defined as a CDAI<150 in the absence of the need for increasing corticosteroid dose or initiation of new therapies for CD during the study period.

The same data elements included in the sCDAI have been combined into two item (stool frequency and abdominal pain) and three item patient reported outcome measures using the original weights derived from the full CDAI referred to as PRO2 and PRO3. Optimum cut-points for CDAI remission were mean daily stool frequency  $\leq 1.5$ , abdominal pain  $\leq 1$ , and general well-being score of  $\leq 1$  (areas under the ROC curve 0.79, 0.91 and 0.89, respectively). PRO2 and PRO3 values corresponding to CDAI scores of 150, 220, and 450 points were 8, 14, and 34 and 13, 22, and 53 respectively, and the corresponding values for CDAI changes of 50, 70, and 100 points, were 2, 5, and 8 and 5, 9, and 14, respectively. We will examine the individual components of these PROs to determine the proportion of each group that met the optimum cutpoint for remission that met the PRO2 definition of remission. Finally, we will determine the proportion of each group with a reduction in the PRO2 and PRO3 that corresponds to 100 point reduction in the CDAI.

The Patient Reported Outcome Measurement System (PROMIS) questionnaire contains several measures previously shown to correlate with disease activity and to have construct validity in CD. These include measures of fatigue, pain interference, social aspects, and sleep.

A subset of core variables found in the Multi-dimensional Health Assessment Questionnaire (MD-HAQ) will be used to assess physical function and joint pain as well as a RADAI Arthritis screening questionnaire.

We will screen for inflammatory back pain using criteria developed by Sieper et al. and assess symptom severity with the Bath AS Functional index in those who screen positive.

### **8.3 Sample Size and Power Determination**

The study is designed to enroll 97 patients into each of the treatment arms. With 97 participants per group, the study will have 80% to 90% power with a type 1 error of 5% to detect a difference of 20% in effectiveness of the two diets depending on the success rate in the reference arm. Our PPRN Patient Governance Council met and determined that a smaller difference is unlikely to justify the challenges of following a strict restriction diet.

### **8.4 Statistical Methods**

A formal data analysis plan will be prepared as a separate document. The following sections summarize the planned analyses.

#### **8.4.1 Baseline Data**

The initial analyses will utilize descriptive statistics to define the characteristics of the study cohort. Continuous variables will be described as medians and interquartile ranges. Categorical variables will be defined as proportions. Formal statistical comparisons of these descriptive variables will be performed comparing the two arms of the study using the Wilcoxon rank sum test for continuous variables and the chi squared or Fisher's exact test for categorical variables. Because any unbalance in the two groups is by definition a chance occurrence, these analyses will be used to highlight areas of substantial unbalance between the study arms.

#### **8.4.2 Efficacy Analysis**

Analysis of the primary outcome: The primary analyses for the RCT will use 2-sided tests of statistical significance and will be performed using the intention-to-treat principle. Thus, patients will be classified according to the study arm that they were assigned, regardless of the amount of food from the assigned diet consumed. The primary analysis will compare the proportion of patients who achieve a symptomatic remission (aim 1) at week 6 using the Cochran-Mantel-Haenszel (CMH) chi square test, which is equivalent to the score test derived from the conditional logistic regression. All patients who are withdrawn or lost to follow-up prior to week 6 will be considered treatment failures. The MSD will be considered the reference group for all analyses. Although randomization should minimize unbalance between the groups, it is still possible that unbalance may occur. As such, we will use stratified analyses and logistic regression analysis to adjust for potential unbalance between the two groups as observed in

the descriptive analyses. Age, sex, smoking status, duration of CD, presence of disease involving the colon and/or rectum, use of corticosteroids during the trial, current use of biologic therapy, and current use of immunomodulator therapy will be examined individually for potential confounding of the main outcome using logistic regression analysis. All variables that affect the crude estimate of the relative risk of effectiveness by 10% or greater will be included in the final model.

Stratified analyses will be used to assess for treatment effect heterogeneity based on the following variables: presence of documented inflammation at baseline (defined as FCP>250 mcg/g, hsCRP >5 mg/L). Although pre-specified, we have not powered the study for these subgroup analyses and as such they will be considered hypothesis generating. Therefore, we will report the overall results as well as results for each subgroup. We note that the strongest a priori hypothesis for treatment effect heterogeneity is with the presence or absence of inflammation. We hypothesize that the SCD may appear relatively more effective among those patients without active inflammation than among those with confirmed active inflammation at baseline.

